- Study follow-up will occur on Week 6, two weeks after the last dosing of MTX.
- Blinding: The study will be partially blinded. The patient and investigator will be blinded as to whether TK-112690 or placebo is administered. The CRO,sponsor, and site pharmacist will know whether the patient was administered active drug or placebo.

Main Study Endpoints/Outcomes

• Mucositis Outcomes

Mucositis status in the patients will be evaluated using 4 different published and validated mucosit scales: OMAS/Sonis, PROMS, WHO, and CTCAE/mucositis.

• Surrogate Marker Outcomes

Plasma samples will be obtained to determine surrogate markers of mucositis, eg, CD40/CD40. TNF- α , etc.

• Safety Outcomes

Adverse events will be assessed throughout the study. Incidents of toxicity will be determined to at least possibly related to the study drug and graded according to CTCAE Version 4.0.

Study Procedures and Study Assessments

- A review of a patient's medical history including a detailed history of the patient's cancer and concomitant medications will be performed at screening.
- Screening for drugs of abuse will be performed at the time of patient screening and Day 0 (the day before start of study).
- Vital sign measurements will be performed at patient screening, on Day 0, and at 24 and 48

hours post each initial infusion of TK-112690/placebo as well as on Day 1 of Week 6.

- Physical examinations will be performed at screening, on Day 0, and 24 and 48 hours post each initial infusion of TK-112690/ placebo as well as on Day 1 of Week 6.
- ECOG performance status will be determined at patient screening, on Day 0, and at Day 1 of Weeks 6.
- For pre-menopausal females, a urine pregnancy test will be performed at screening, on Day 0, and at Day 1 of Week 6.
- 12-Lead ECG at screening and 24 hours post each initial infusion of TK-112690/ Placebo.
- CBC, Liver function test, Kidney function test determination at the clinical site prior to methotrexate treatment to ensure patient fit to dose.
- Serum chemistry, hematology, coagulation and urinalysis at screening, Day 0, and at 24 and 48 hours post each initial infusion of TK-112690/ placebo as well as on Day 1 of Week 6.
- Adverse events will be evaluated 5, 24 and 48 hours post each initial infusion of TK-112690/ Placebo as well as on Day 1 of Week 6.

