- Subjects that have participated in any other investigative clinical trial in the past 4 weeks.

Dose and Dosing Regimen

The dose of METREXASSISTTM (TK-112690) will be 45 mg/kg administered parenterally over one hour in a clear, neutral, aqueous formulation (no organic chemical excipients). METREXASSISTTM will be given one hour before and 5 hours after the MTX treatment. The nutrient drink will be given one hour before METREXASSISTTM infusion. The MTX formulation will that traditionally used as standard-of-

care at a study site.

Test Product, Dose and Mode of Administration

- METREXASSISTTM (TK-112690 for Infusion) is a clear, sterile, neutral (pH=7.4), aqueous solution containing 5 mL of 100 mg/mL TK-112690.
- METREXASSISTTM is packaged as a 5 mL solution in a 10 mL flint glass vial with an elastomeric stopper held in place by an aluminum seal and flip-off cap. The concentration of TK-112690 in the solution is 100 mg/mL
- METREXASSISTTM will be administered as a continuous iv infusion over a duration of one hour in a volume of 250 mL normal saline.
- The nutrient drink, Fortasyn Connect[™] / Souvenaid[™], is commercially available as a 125 mL, 125 kcal solution. The drink is administered orally.
- The placebo is isotonic saline.

Reference Therapy or Comparator

Placebo-Isotonic saline

Follow-up

[figure not shown]
Subjects need to return at Day 1 of Week 6, which is two weeks from the last dose of the study drug.

Statistical Methods

- Safety: AEs, vital signs, physical examination data and clinical laboratory data will be analyzed using descriptive statistics with safety outcomes for patients in a dose group pooled & compared with patients in other groups.
- Mucositis: Scale data from individual doses groups will be analyzed using descriptive statistics.
- Surrogate Markers: Plasma concentration data evaluated for individual doses groups using descriptive statistics as well as compared with Surrogate marker data from the completed Phase 1bstudy.

INTRODUCTION

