7.1. SCHEDULE OF EVENTS

Schedule of events are provided in **Table 12 below**. **Table 12.** Schedule of events (weekly cycle for 4 weeks and follow up at 6 week)

Englishting	Samooning	D. 0	Weeks 1, 2, 3, and 4					Week 6
Evaluation	Screening	Day 0	0h	5h	6h	24h	48h	Follow-up

Informed Consent ¹	Х							
I/E Criteria	Х							
Medical history ²	Х							
Test for drugs of abuse	Х	Х						
Physical examination ^{3,4}	Х	Х				X ⁵	X ⁵	Х
Vital signs and weight	Х	Х				X^6	X ⁶	X^6
ECOG	Х	Х						Х
Pregnancy test (females)	Х	Х						Х
12-Lead ECG	Х					Х		
Laboratory tests ⁷	Х	Х				Х	Х	Х
Randomization		Х						
CBC, Kidney function test, Liver Function test		X^8						
Nutritional supplement			X ⁹					
TK-112690/placebo treatments ¹⁰			X^{10}		X ¹³			
MTX treatment			X ¹¹					
Surrogate marker sample			X ¹²	Х		Х	Х	Х
Mucositis evaluation ¹⁴		Х				Х	Х	Х
Disease Status	Х							Х
AEs assessment				Х		Х	Х	Х
1 To be obtained before any	study-related	activities at	e perform	-d				

¹ To be obtained before any study-related activities are performed.

² Include a review of previous/ongoing medications for 180 days prior to enrollment.

³ Complete examination, including assessments of the skin, head, eyes, ears, nose, throat, neck, thyroid, lungs,

heart, abdomen, lymph nodes, extremities, and body weight.

⁴ Height will be measured at screening only.

⁵ Partial examinations to update findings from the examination performed at screening.

⁶ Include blood pressure, pulse, respiratory rate and temperature.

⁷ Includes serum chemistry, hematology (including coagulation), urinalysis; Hepatitis B/C & HIV only at screening

⁸ CBC, Kidney function test, Liver Function test at clinical site can be performed anytime within 24 hours of a methotrexate treatment (NEEDED FOR ALL MTX TREATMENTS, EG, TREATMENTS ON WEEKS 1, 2, 3, AND 4, TO VERIFY OK TO DOSE MTX)

⁹One hour before TK infusion/placebo

¹⁰ Beginning of TK-112690/placebo infusions is 0 hours. Dose is 45 mg/kg.

^{11 45} mg/m² one hour after TK-112690/placebo infusion.

¹² Pre-dose control samples for surrogate marker measurements.

¹³6 hours after TK-112690/placebo treatment, ie, 5 hours post MTX treatment

¹⁴See Section 20.6 for mucositis assessment scales.

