7.1.4. Follow-Up Evaluations

All patients will undergo the following on Day 1 of Week 6:

- Perform a physical examination and determine vital signs, weight, and AE assessment.
- Determine ECOG performance status.
- For females of childbearing age, a pregnancy test will be performed.
- Perform laboratory tests (hematology, chemistry, coagulation and urinalysis).
- Obtain a blood sample for surrogate marker evaluation.
- Disease (tumor) assessment by CT scanning will be performed.
- Mucositis assessment (Section 20.6, Appendix 6).

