9.1.4. Follow-up of Adverse Events

All adverse events (and treatments for them) must be documented throughout the Study Treatment Phase starting after the administration of the first dose of study medication and for 28 days after the last intake of study medication, and followed up/medically managed until the event is either resolved or adequately explained, even after the subject has completed his/her study treatment. Unrelated, mild or moderate events must be followed for 28 days after the last study drug administration. Serious, life threatening or related events must be followed until resolution, the subject's death, the start of a new cancer therapy or the relationship is re-assessed.

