Any pregnancy diagnosed during the study, or that occurs within 28 days after stopping study medication, must be reported immediately to the PI. The PI will notify the sponsor or designee. The outcome of all such pregnancies (i.e., spontaneous miscarriage, elective termination, normal birth, or congenital abnormality) must be documented and followed-up on a form that will be provided by the sponsor. The pregnancy will be followed to term and the outcome, including any premature termination, must be reported to the sponsor. All live births must be followed for a minimum of 30 days or to the first well-baby visit. All reports of congenital abnormalities/birth defects and spontaneous abortions/miscarriages should be reported as an SAE for this study. Elective abortion procedures, without complications, should not be considered as adverse events.

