A serious adverse event occurring during the study or which comes to the attention of the investigator within 28 days after stopping the treatment or during the protocol defined follow-up period, if this is longer, whether considered treatment related or not, must be reported. In addition, a SAE that occurs after this time, if considered related to test "drug," should be reported.

Progression of neoplasia should not be reported as an AE or SAE. Findings that are clearly consistent with the expected progression of the underlying cancer should not be reported as an AE, and hospitalizations due to the progression of cancer do not necessarily qualify for a SAE. If there is any

uncertainty about a finding being due solely to progression of neoplasia, the finding should be reported as an AE or SAE as appropriate.

Such preliminary reports will be followed by detailed descriptions later, which will include copies of hospital case reports, autopsy reports and other documents when requested and applicable.

For SAEs, the following must be assessed and recorded on the adverse event page of the CRF: intensity, relationship to test substance, action taken, and outcome.

The investigator must notify the Ethics Review Committee/Institutional Review Board of a SAE in writing as soon as is practical and in accordance with international and local laws and regulations.

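### Adverse events are to be documented for 28 days after the last dose, but the last scheduled contact falls 14 days after it, so new events in the second half of the window have no planned ascertainment in an on-schedule completer.

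*Combined protocol and SAP*

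**What the plan says.** **The window.** Section 9.1.4 requires every AE to be documented "starting after the administration of the first dose of study medication and for 28 days after the last intake of study medication". It adds a follow-up rule for lesser events: "Unrelated, mild or moderate events must be followed for 28 days after the last study drug administration". The same length recurs for serious AEs (SAEs) in Appendix 5 ("within 28 days after stopping the treatment or during the protocol defined follow-up period", whichever is longer) and for pregnancies in section 9.1.6 ("or that occurs within 28 days after stopping study medication").

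**The schedule.** The follow-up paragraph of the synopsis reads: "Subjects need to return at Day 1 of Week 6, which is two weeks from the last dose of the study drug". The synopsis design section agrees: "Study follow-up will occur on Week 6, two weeks after the last dosing of MTX". Section 7.1.4 opens with "All patients will undergo the following on Day 1 of Week 6" and lists an AE assessment among the procedures. Table 12 has no column after Week 6.

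**How events are found.** AE assessments are scheduled at 5, 24 and 48 hours after each initial infusion and at Week 6 (synopsis, Table 12). Section 9.3 has the investigator question the patient about AEs at each visit. After Week 6 the only further visits are the monthly ones in section 8.2, for patients with a continuing toxicity that appears to be caused by the drug.

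**The concern.** The stated window is twice as long as the interval over which the plan arranges to look. The Week 6 visit can pick up, by recall, what happened between the last dose and that day. Nothing planned does the same for the two weeks that follow. A new non-serious event in that period is recorded only if the patient volunteers it, although section 9.1.4 says that it must be documented.

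Safety and tolerability are the secondary objective (section 2.2), and section 10.3.1 tabulates treatment-emergent AEs by arm without defining the time window for the tables. With 11 patients per arm, a few unrecorded events can change an incidence visibly. A reader who takes 28 days from section 9.1.4 would assume that the counts cover a period that was not actively observed.

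**Working it through.** **Inputs**
- Weekly dosing in Weeks 1 to 4 and one follow-up on Day 1 of Week 6: synopsis, Table 12, section 7.1.4. Dosing is taken to fall on Day 1 of each week.
- AE window of 28 days after the last dose: section 9.1.4.
- Dosing tolerance of one day either way: section 5.3.
- Treatment may be withheld for up to two weeks before permanent discontinuation: section 3.1.2. Further treatments are possible at the investigator's discretion: section 10.3.

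**Reproducing the plan's own interval**

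Study day = 7 × (week − 1) + day.
- Last dose, Week 4 Day 1: 7 × 3 + 1 = Day 22.
- Follow-up, Week 6 Day 1: 7 × 5 + 1 = Day 36.
- Interval: 36 − 22 = 14 days, which matches the two weeks in the synopsis.

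**Uncovered part of the window, on-schedule completer**
- Window end: 22 + 28 = Day 50.
- Days after the last scheduled contact: 50 − 36 = 14 (Days 37 to 50).
- Share: 14 / 28 = 50%.

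**Sensitivity to the date of the last dose**

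| Situation | Last dose | Window end | Days after the Week 6 visit |
|---|---|---|---|
| One day early | 21 | 49 | 13 (46%) |
| On schedule | 22 | 50 | 14 (50%) |
| One day late | 23 | 51 | 15 (54%) |
| One-week delay, visit fixed at Day 36 | 29 | 57 | 21 (75%) |
| Two-week delay, visit fixed at Day 36 | 36 | 64 | 28 (100%) |
| Last dose in Week 3, attends Week 6 | 15 | 43 | 7 (25%) |
| Last dose in Week 2, attends Week 6 | 8 | 36 | 0 |
| Last dose in Week 1, attends Week 6 | 1 | 29 | 0 |

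In the two-week-delay row, the 48-hour check after that dose (Day 38) would be the last contact, leaving 64 − 38 = 26 days. If the follow-up visit instead moves with the last dose, the delayed rows return to 14 days. The documents do not say which applies. They also do not say whether withdrawn patients attend Week 6; section 8.2 lists assessments at the time of withdrawal only. A patient seen only then could have most of the 28 days uncovered.

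**How many might leave early.** In Phase 1b, 14 of 19 men and 2 of 6 women completed (section 1.5.2), that is 16 of 25. If the same rate applied here, 22 × 9 / 25 = 7.9, or about 8 patients, would not complete. This is an assumption, because the Phase 1b doses and design differ.

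**The case against.** **Other provisions reach past Week 6.** Section 9.1.4 follows open unrelated mild or moderate events to 28 days, and serious, life-threatening or related ones longer. Section 9.1.5 repeats unexplained abnormal laboratory values. Section 9.3 requires volunteered events to be reported. Section 8.2 brings back patients with continuing toxicity. So a reader should not infer that Week 6 is the last contact of any kind, or that nothing is captured afterwards. What remains is that each of these depends on an event already open, an abnormal value already found, or a patient who speaks up. None of them looks for new events.

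**SAE and pregnancy rules are passive by design.** Appendix 5 covers events that the investigator learns of, and section 9.1.6 relies on notification, so the absence of a visit does not contradict them. This stands. The conflict rests on the general AE duty in section 9.1.4. The opening of section 9.3.3 on SAE reporting is missing from the text I had, which is another reason not to rest it on SAEs.

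**The gap is not the same for everyone.** It would be tempting to apply 14 days to all 22 patients. Early withdrawal, delay and extension give different figures, as the table shows.

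**The harm is not quantified.** A reader might infer that late cytopenia or infection would be missed. The documents report such events in Phase 1b but give no onset times, and no rate for Days 37 to 50. The drug's half-life is put at about 4 to 6 hours (section 1.5), so 14 days is at least 336 / 6 = 56 half-lives, and half of the days need not be half of the drug-related risk. This also stands. It does not remove the conflict, because the protocol chose 28 days itself and section 9.1.1 asks for AEs regardless of cause.

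**Both arms share the schedule.** A differential bias between arms cannot be inferred. Capture will be uneven between patients with and without open events, but the main effect is under-counting in both arms.

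**Conclusion.** The schedule does not deliver the 28-day window that the protocol sets. For a patient who receives four doses on schedule and attends on Day 36, 14 of the 28 days (13 to 15 with the one-day dosing tolerance) have no scheduled ascertainment of new-onset AEs. SAEs and pregnancies in those days are captured only passively. For other patients the figure runs from 0 to 28 days by calendar arithmetic, and the documents do not settle which case applies after a delay or a withdrawal.

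The consequence is a risk of under-counting new events in both arms, of a size that the documents do not allow one to estimate. It bears on the secondary safety objective and on how the AE tables may be described. It does not touch the primary efficacy comparison. It should be corrected because the conflict is exact and the remedy is cheap.

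**What to change.** Add to Table 12, section 7.1.4 and section 8.2 one telephone contact 28 days after each subject's own last dose of study medication, including subjects who withdraw. It should ask about new AEs, SAEs, pregnancy and new medication. For an on-schedule completer this falls on Day 50 and brings the uncovered part of the window from 14 days to 0. Tying it to the subject's own last dose also handles delays, extensions and early stopping. The cost is about 22 calls (about 30 if the 8 additional subjects in section 3.5 are enrolled) and roughly two more weeks of follow-up per completer.

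If the sponsor declines, reconcile sections 9.1.4 and 9.1.6, Appendix 5 and Table 12 in one amendment. Changing section 9.1.4 alone would leave the 28-day limits for SAEs and pregnancies out of step with it. Section 10.3.1 should then label the AE tables, for both arms, as actively ascertained only through Week 6. This costs wording only, but gives up active observation of the later two weeks.

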9.1.5. Follow-up of Abnormal Laboratory Values

In the events of unexplained abnormal laboratory test values, the tests should be repeated and followed up until they have returned to normal range or to the baseline value, and/or an adequate explanation of the

abnormality is found. If a clear explanation is established it should be recorded on the CRF.

9.1.6. Pregnancy

Pregnancy, in and of itself, is not regarded as an adverse event, unless there is suspicion that study medication may have interfered with the effectiveness of a contraceptive medication or method. The procedures that will be followed based on whether a pregnancy is confirmed by a positive serum or urine test result are listed below:

- Pregnancy confirmed by a positive serum test result, then:
 - PI and subject must notify each other immediately
 - PI must notify the sponsor immediately
 - Discontinue study medication immediately
 - Withdraw the subject from the study
 - Perform the required Early Termination visit study evaluations
 - PI must complete and submit the initial and follow-up report to the sponsor
 - Pregnancy confirmed by a positive urine test result, then:
 - PI and subject must notify each other immediately
 - PI must notify the sponsor immediately
 - Study medication must be discontinued immediately
 - A serum pregnancy test must be performed to confirm the urine test result. (The serum test should be performed at the investigative site to ensure the test will be performed promptly and the result available immediately for review)
- If a positive serum test confirms the urine test result, then:
 - Withdraw the subject from the study
 - Perform the required Early Termination visit study evaluations
 - PI must complete and submit the required initial and follow-up report to the sponsor
- If a negative serum test does not confirm the urine test result, then:
 - The PI will use his/her expert judgment, based on an assessment of the potential benefit/risk to the subject, to determine if it is in the subject's best interest to resume study medication and continue participation in the study

Any pregnancy diagnosed during the study, or that occurs within 28 days after stopping study medication, must be reported immediately to the PI. The PI will notify the sponsor or designee. The outcome of all such pregnancies (i.e., spontaneous miscarriage, elective termination, normal birth, or congenital abnormality) must be documented and followed-up on a form that will be provided by the sponsor. The pregnancy will be followed to term and the outcome, including any premature termination, must be reported to the sponsor. All live births must be followed for a minimum of 30 days or to the first well-baby visit. All reports of congenital abnormalities/birth defects and spontaneous abortions/miscarriages should be reported as an SAE for this study. Elective abortion procedures, without complications, should not be considered as adverse events.

9.2. Assessing, Recording, and Analyzing Safety Parameters

Safety lab assessments will be performed by the central laboratory and will be collected and processed according to standard investigative site procedures. Normal value ranges and laboratory certification will be collected from all laboratories prior to study initiation.

Safety laboratory assessments will include:

- Complete Blood Count with differential
- Enzyme panel including AST, ALT, LDH, creatinine kinase, alkaline phosphatase
- Chemistry panel including total protein, albumin, total bilirubin, uric acid, phosphate, triglycerides, cholesterol, calcium, BUN, creatinine, sodium, potassium, chloride, bicarbonate, glucose, and phosphorus; and
- Urinalysis including pH, glucose, protein, ketones and blood

9.2.1. ECG Parameters

ECG parameters will be analyzed including ECG abnormalities and PI's assessment of clinical significance analyzing above parameters, rhythm abnormalities, and conduction abnormalities. Any abnormalities will be reported on the CRF with a copy of the ECG recording.

9.3. RECORDING AND REPORTING ADVERSE EVENTS/INTERCURRENT ILLNESSES

The PI will probe, via discussion with the subject, for the occurrence of AEs during each subject visit and record the information in the site's source documents. For each AE, the PI should note the start and resolution dates, the severity, whether it meets the definition of an SAE, the relationship of the event to the study drug, the action taken regarding study drug, and the outcome of the event. Data should be transcribed from the source documents to the case report forms as per the case report form instructions, so that all changes in intensity and seriousness will be captured on the AE case report form.

The PI must report in detail all adverse signs and symptoms which are either volunteered by subjects or observed during or following the course of Investigational product administration on the appropriate CRF page.

All AEs will be monitored until resolution or, if the AE is determined to be chronic, a cause is identified. If an AE is considered possibly related to study treatment and remains unresolved at the conclusion of the study, this event will be followed until resolution, stabilization, or initiation of treatment that confounds the ability to assess the event.

